12.2 Documentation

All adverse events must be documented in detail within the medical record. The patient will be observed and monitored carefully until the condition resolves, stabilizes, or its cause is identified. All adverse events, including laboratory abnormalities, will be followed up according to good medical practices. Information to be recorded includes the following:

a. Specific type of reaction.

b. Duration of reaction.

c. Severity/grade of reaction according to the NCI Common Terminology Criteria for Adverse Events v4.0 (CTCAE).

d. Suspected cause of the reaction (i.e. possibly or probably related to one of the following: study treatment, progression of disease, concurrent medications, concurrent illness, or other factors).

e. Changes made in the administration of the study drugs and other actions taken to alleviate the clinical event.

f. Patient's response to medical interventions.

12.3 Reporting

According to FDA regulations (21 CFR 312.32), IND safety reports shall address "any adverse

experience associated with the use of a drug that is both serious and unexpected." The IRB will be notified of any adverse event fulfilling the following criteria:

12.3.1 The adverse event is **SERIOUS** (as defined above),

or

12.3.2 The adverse event is not serious, but is **UNEXPECTED** and its association with the study drug, device, or research-related procedure is either **DEFINITELY**, **PROBABLY**, or **POSSIBLY RELATED**, or **UNKNOWN** (as defined above).

Federal policy [45 CFR 46.116(b)(5)] also requires that investigators inform subjects of any important new information that might affect their willingness to continue participating in the research. When an adverse event necessitates changes to the consent/assent form(s) and/or protocol, or that notification is given to currently or previously enrolled subjects, an amendment request will be submitted in conjunction with the adverse event report. The IRB will make a determination whether any new findings, new knowledge, or adverse effects should be communicated to subjects.

In accordance with IRB guidelines, serious adverse events will be reported within 10 days of learning of the event to the Office of Research Risks Protection, [name], CAMPUS, [contact] telephone, [name] fax, Email: [contact], using the Event Reporting Form (http://orrp.osu.edu/irb/event/documents/EventReportingForm v2.2.doc) of The Ohio State University Institutional Review Boards. If the adverse event involved the death of a subject, it will be reported immediately, usually within 72 hours. Deaths from "natural causes" or underlying disease that occur more than 30 days following completion of study interventions (i.e., events not temporally associated) need not be reported. Unexpected adverse events that are not serious but may be associated with the drug, device, or procedure (see below) should generally be reported to the IRB within 30 days of notification of the event.

In some instances, adverse events or "unanticipated problems" result in social or psychological harm rather than physical harm to subjects or others. These events should also be reported to the IRB within 30 days, unless they are considered "serious". A letter format may be used for reporting these events instead of the Event Reporting Form, as applicable.

The IRB will review all serious adverse event reports to reevaluate the risks and benefits of the research and need for changes. All other reportable adverse events (unexpected and related or unknown) will be reviewed administratively, unless IRB review is recommended. All investigators will be notified of any action taken, usually within 30 days.

13. CRITERIA FOR RESPONSE ASSESSMENT

All patients who took the intervention for any period of time will be considered evaluable. Participants with only baseline measures and who did not receive the intervention will be considered as drop-outs. RECIST v. 1.1 will be utilized to evaluate responses to therapy.

14 STUDY CALENDAR

	Week				
Tests & observations	0	4	8	12	16
Signed informed consent	Х				
History and Physical Exam	Х				Х
Height/weight	Х	Х	Х	Х	Х

Standard of Care Imaging	Х		X		X
Continuous Glucose/Ketone Monitoring	Х		Х		Х
Ketone Finger Stick	Х	Х	Х	Х	Х
Activity Tracker	Х	Х	Х	Х	Х
DXA Bone & Body Fat Quantification	х				x
Cognitive Testing	Х		Х		X
Review of medications	Х	Х		Х	
Performance status	Х		Х		Х
SF-36	Х			Х	
Brief Pain Inventory Questionnaire (BPI-10)	х		х		х
Brief Fatigue Inventory	Х		Х		Х
FACT Questionnaire	Х		Х		Х
Hearth Hope Index	Х		Х		Х
Blood tests	Х		Х		Х
FFQ questionnaire/3-day food log*	х				

15 CRITERIA FOR REMOVAL OF PATIENTS FROM PROTOCOL THERAPY

Study patients may voluntarily withdraw at any time from the protocol. If a treating physician elects to remove a patient from the study, the Principal Investigator must be notified of withdrawal from the protocol. The reasons for discontinuation of the study must be documented in the patient record and data collection forms. Patients experiencing irreversible Grade 3-4 toxicity that is clearly related to the study treatment will be removed from the protocol. Patients with documented progression of disease will be removed from the protocol.

16 ETHICAL AND REGULATORY CONSIDERATIONS

This trial will be conducted in compliance with the protocol, Good Clinical Practice guidelines, and all applicable regulatory requirements.

16. 1 Institutional Review Board

The Principal Investigator will have obtained written approval to conduct the study from The Ohio State University IRB and the Clinical Scientific Review Committee of the James Cancer Hospital and Solove Research Institute. All amendments must be approved by the Institutional Review Board of The Ohio State University prior to implementation.

16.2 Informed consent

All potential candidates for the study will be given a copy to read of the consent form for the study. The Principal Investigator and/or designee will explain all aspects of the study in lay language and answer all the candidate's questions regarding the study. If the candidate desires to participate in the study, she will be asked to sign the Informed Consent. The study agent will not be released to a subject without a signed Informed Consent.

Elements of informed consent include explanations of 1) the purpose of the trial, 2) what the study

entails, 3) alternate treatments, 4) expenses and inconveniences to be incurred, 5) discomfort and risks to the subject, 6) whether she will receive payment for participation in the study, 7) contact person to call in the event of an emergency, 8) subject rights as a result of illness or injury from trial participation, 9) her right to withdraw from the trial at any time without prejudice, 10) confidentiality of trial participation.

16.3 Patient confidentiality

The information obtained during the conduct of this study is considered confidential and will not be released without the written permission of the subject, except as necessary for monitoring by the FDA or other regulatory agencies. All laboratory specimens will be labeled with coded identifiers in order to maintain confidentiality. Signed consent forms, data sheets, and laboratory notebooks will be kept in locked cabinets in [name] or [name] office and/or research laboratories.

16.4 Publication of research findings

Publications of the research findings will present data in a format that will not reveal the identity of the participants.

16.5 Compliance monitoring

In accordance with IRB guidelines, the study program will be reviewed by the IRB every 12 months or less. Deviations from the protocol must be documented in the medical record and reported immediately to the PI. Deviations that meet the criteria for Immediate Event Reporting (http://orrp.osu.edu/irb/event/index.cfm) such as those that increase risks to subjects and/or compromise scientific integrity will be reported immediately to the IRB.

16.6 Biosafety

This project will involve the use and analysis of human cells and tissues. Specific precautions will be taken to protect laboratory personnel and support personnel form possible infective agents from these samples, with the goals of containment of biological materials, proper waste disposal, routine decontamination of equipment and surfaces, and implementation of procedures for accidents.

16.7 Data Safety Monitoring Plan

The data and safety monitoring plan will involve the continuous evaluation of safety, data quality and data timeliness. Investigators will conduct continuous review of data and patient safety at their regular Disease Group meetings (at least monthly) and the discussion will be documented in the minutes. The Co-PIs of the trial will review toxicities and responses of the trial where applicable at these disease center meetings and determine if the risk/benefit ratio of the trial changes. Frequency and severity of adverse events will be reviewed by the Co-PIs and compared to what is known about the agent/device from other sources; including published literature, scientific meetings and discussions with the sponsors, to determine if the trial should be terminated before completion. Serious adverse events and responses will also be reviewed by the OSUCCC Data and Safety Monitoring Committee (DSMC). The Co-PIs will also submit a progress report biannually that will be reviewed by the committee per the DSMC plan. All reportable Serious Adverse Events (SAE) will also be reported to the IRB of record as per the policies of the IRB.

17.0 STATISTICAL ANALYSES

Analysis Plan

Unless otherwise specified, all analyses will proceed on an intent-to-treat basis, and hypothesis tests will be two-sided and at the 5% significance level.

The primary objective is to assess the feasibility of maintaining a ketogenic versus AICR diet in patients with brain metastasis selected for radiosurgery. The primary measurements are blood levels of glucose and ketones. Measurements will be taken at baseline, 8 weeks, and 16 weeks. These biomarker outcomes will be analyzed using mixed effects linear regression with fixed effects for timepoint, diet group, their interaction, BMI, and sex. We will use subject-level intercept random effects to account for correlation between repeated measurements within subjects. The primary targets of inference are the treatment effects at each (post-baseline) timepoint. To test the two primary measurements at the two post-baseline timepoints, we will use a 4-way Bonferroni-Holm correction to account for multiplicity. Retention at week 8 and 16, as well as side effects, will be summarized and compared between diet groups.

To assess the preliminary efficacy of ketogenic versus AICR diet on tumor response to targeted radiation therapy, we will use a Chi-squared test for the association between treatment group and partial-or-complete response according to RECIST v1.1.

For the exploratory objective assessing the preliminary effects of the ketogenic versus AICR diet on quality of life in BM individuals undergoing radiation therapy, we will use the same linear mixed effects model as for the primary objective, but with the following quality-of-life endpoints as outcomes: Hearth Hope Index, SF-36, FACT-B, Brief Pain Inventory, and Brief Fatigue Inventory. Tests will be performed without multiplicity correction.

The mixed models used for the primary analyses are applicable to unbalanced data due to chance imbalances, missing data, or drop-out. We will assess the possible impact of non-random missingness using sensitivity analyses.

Power Analysis

We base our power analysis on preliminary data from a single-arm trial involving patients with Stage IV disease undergoing treatment plus a ketogenic diet. The changes in blood glucose from baseline to 3 months have mean 11.25 mg/dL and standard deviation 1.077 mg/dL, and the changes in blood ketone levels have mean 0.6 mmol and standard deviation 0.16 mmol. With 12 completers per arm and a significance level of 0.0125 to account for multiplicity, a two-sample t-test has 99% power to detect differences in mean changes between diet arms of 2.3 mg/dL in glucose levels and 0.34 mmol in ketone levels. We expect our tests based on linear mixed models to have slightly higher power.

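### The primary mixed model makes no use of the patient's baseline glucose or ketone value and leaves open whether the tested effect is an arm difference at the visit or the powered difference in change

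*Protocol*

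**What the plan says.** Section 17.0 of the protocol sets the schedule for the two primary measurements, glucose and ketones: "Measurements will be taken at baseline, 8 weeks, and 16 weeks". They are analysed by "mixed effects linear regression with fixed effects for timepoint, diet group, their interaction, BMI, and sex". For the covariance, "We will use subject-level intercept random effects to account for correlation between repeated measurements within subjects". The inferential target is given as follows: "The primary targets of inference are the treatment effects at each (post-baseline) timepoint". The coefficient or contrast is not named. Tests are two-sided at 5%, and for two measurements at two visits "we will use a 4-way Bonferroni-Holm correction to account for multiplicity".

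The Power Analysis in the same section uses a two-sample t-test on change from baseline: "With 12 completers per arm and a significance level of 0.0125 to account for multiplicity", it claims 99% power for arm differences in mean change of 2.3 mg/dL (glucose) and 0.34 mmol (ketones). It adds: "We expect our tests based on linear mixed models to have slightly higher power".

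The Dietary Interventions paragraph that follows Section 7.3.6 has both arms start their assigned meals four to seven days before baseline testing, so that the ketogenic arm is already in ketosis at baseline.

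**The concern.** Baseline appears to be one of the response timepoints, and the arm means are free there. Two contrasts can then be read as the treatment effect at week 8 or 16:

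- diet group plus interaction, which is the arm difference at that visit;
- the interaction alone, which is the arm difference in change from baseline.

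Neither adjusts for the patient's own starting value, although BMI and sex are adjusted for. The wording points more naturally to the first, while the power sentence concerns the second. The visit difference carries the full between-patient spread. With 12 patients per arm, the stated 99% may therefore not describe the test that is run.

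BMI is also not fixed at baseline in the model. The Study Calendar records weight at every visit, and the Dietary Interventions paragraph expects weight loss in overweight participants on the ketogenic diet. A time-varying BMI would adjust for a consequence of the diet.

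**Working it through.** **Inputs from Section 17.0.** 12 per arm; two-sided alpha 0.05/4 = 0.0125; SD of change 1.077 mg/dL and 0.16 mmol; differences 2.3 mg/dL and 0.34 mmol.

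**Assumption.** The within-patient correlation rho is not in the protocol. It is taken here from 0.3 to 0.9, with equal variance at all visits and equal correlation between them, as a random intercept implies. Since the model includes BMI and sex, rho is the correlation left after them.

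**1. The plan's own figure.** SE = SD x sqrt(2/12).

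- Glucose: 1.077 x 0.4082 = 0.4397; 2.3/0.4397 = 5.23. Noncentral t with 22 df gives 99.05%.
- Ketones: 0.16 x 0.4082 = 0.0653; 0.34/0.0653 = 5.21, giving 98.99%.

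The stated 99% reproduces.

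**2. If the interaction is tested.** It is the difference in mean change, with the same SE. The random-intercept model gives it about (24 - 2) x (3 - 1) = 44 df. Power is 99.45% for glucose and 99.41% for ketones, so the expectation of slightly higher power holds.

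**3. If the visit difference is tested, and if a pre-diet baseline is adjusted for.**

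- SD of change = visit SD x sqrt(2(1 - rho)), so visit SD = 1.077/sqrt(2(1 - rho)).
- Baseline-adjusted SD = visit SD x sqrt(1 - rho^2), which equals 1.077 x sqrt((1 + rho)/2).

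Power for 2.3 mg/dL glucose at alpha 0.0125 (22 df for visit, 21 df for adjusted):

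| rho | visit SD | visit power | adjusted SD | adjusted power |
|---|---|---|---|---|
| 0.3 | 0.910 | 99.9% | 0.868 | 99.97% |
| 0.5 | 1.077 | 99.05% | 0.933 | 99.9% |
| 0.6 | 1.204 | 96.7% | 0.963 | 99.8% |
| 0.7 | 1.390 | 89.6% | 0.993 | 99.7% |
| 0.8 | 1.703 | 71.7% | 1.022 | 99.5% |
| 0.9 | 2.408 | 37.3% | 1.050 | 99.3% |

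Ketones for 0.34 mmol behave the same way: visit power 89.3%, 71.2% and 36.9% at rho 0.7, 0.8 and 0.9, and adjusted power 99.7%, 99.5% and 99.2%.

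Adjusted variance is (1 - rho^2) times the visit variance and (1 + rho)/2 times the change variance. It is below the first unless rho is 0, and below the second for any rho under 1.

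**4. Which baseline can be used.** Suppose the true week-16 ketone difference is 0.34 and an amount b is already present at baseline because the diet has begun (b is an assumption). The adjusted estimate then centres on 0.34 - rho x b, and the change estimate on 0.34 - b.

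| b | adjusted, rho 0.3 | adjusted, rho 0.5 | adjusted, rho 0.8 | change |
|---|---|---|---|---|
| 0 | 0.34 | 0.34 | 0.34 | 0.34 |
| 0.17 | 0.289 | 0.255 | 0.204 | 0.17 |
| 0.34 | 0.238 | 0.17 | 0.068 | 0 |

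The visit difference stays at 0.34 throughout. Adjustment, or subtraction, is therefore sound only with a value taken before the diet starts.

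**The case against.** **The model contains the powered contrast.** With baseline among the timepoints, the interaction is exactly the difference in mean change, and on that reading the analysis and power paragraphs agree. This stands. A reader might infer that the tested contrast is definitely not the powered one, but the protocol leaves the choice open and does not settle it that way.

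**Lower precision is not an error.** Also true. The model with free baseline means is valid. At the stated SD of change, adjustment gains less than one percentage point over the change contrast.

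**Power for glucose might seem to collapse to a few percent.** A reader could infer this by assuming a between-patient SD of, say, 10 mg/dL. Combined with the stated SD of change, that implies rho = 1 - 1.077^2/(2 x 10^2) = 0.994. The protocol gives neither figure, so the inference is not supported. Whether an SD of change of 1.077 is plausible is a separate question.

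**Under the written schedule, not adjusting is safer.** This stands for the scheduled baseline. The Study Calendar has no visit before week 0, and baseline testing comes after several days of assigned meals. On that schedule the visit difference is the contrast least harmed. The same timing damages the powered change contrast more, so a pre-diet value is needed for any analysis that refers to baseline.

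**BMI listed beside sex reads as a baseline covariate.** Probably so; one word removes the doubt.

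**Conclusion.** The point holds as a cheap improvement, not as an error that must be corrected. Section 17.0 lists its fixed effects without a baseline glucose or ketone term, and it does not name the contrast behind the treatment effect at each visit. Under the interaction reading the power statement is right, at about 99.5%. Under the visit-difference reading it holds up to a correlation of about 0.5 and then falls to about 90%, 72% and 37% at 0.7, 0.8 and 0.9. Adjusting for a true pre-diet baseline gives about 99% or more over the whole range, so the claim would no longer depend on an unstated correlation.

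These figures rest on the stated SDs of change, 12 completers per arm, an equal-correlation structure and an assumed rho. The benefit requires a baseline measured before the assigned diet begins; it does not carry over to the baseline now scheduled.

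**What to change.** In Section 17.0:

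- Define the target as the baseline-adjusted arm difference at weeks 8 and 16. Either constrain both arms to a common baseline mean (drop the diet main effect and keep the diet effects at the two later visits), or drop the baseline rows and enter the baseline value as a covariate.
- State that the baseline used is a glucose and ketone value taken before the first study meal, and that an on-diet value is neither adjusted for nor subtracted.
- Write baseline BMI in the covariate list.
- Restate the power sentence for this contrast, with the correlation assumed.

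The cost is a few lines of text, a small change to the model, and one pre-meal measurement per patient, for example a finger stick with the meter already supplied. If no pre-diet value can be obtained, do not adjust for the scheduled baseline. Name the visit difference as the target and give its power over a range of correlations.

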8.2 Adherence

Participant adherence with the study intervention will be encouraged and monitored in several ways. All participants will be provided a handheld glucometer (Precision Xtra, Abbott Nutrition) and reagent strips that measure BOHB from a small amount of blood obtained by finger stick. Although there is variability between people, BOHB levels in individuals consuming more than 100 grams of carbohydrate per day are usually ≤ 0.1 mmol/L. A primary goal of the initial diet intervention is for each participant to enter nutritional ketosis, which starts at 0.5 mM and extends up to approximately 3.5 mmol/L. This is a strong indication that fat is being used as one's primary fuel, and there may be other therapeutic benefits associated with ketones in this range. Transient increases in ketones above 3.5 mmol/L may occur after exercise, but regulatory feedback systems keep ketones from elevating to dangerous levels that are seen in uncontrolled type-1 diabetics who have insufficient insulin (i.e., >10 mmol/L). Participant's information will be kept private and only made available to IRB approved research staff. During the intervals between research- based visits participants will report their ketone levels daily to the research coordinator and lead RD on the team and adjustments to the diet made accordingly.

We will counsel patients to aim for a level > 1.0 mM while following principles of a well-formulated ketogenic diet. If ketone readings are lower than 0.5 mM, we will individually work with the patient to identify appropriate changes to their diet/lifestyle to achieve nutritional ketosis. The monitoring of daily ketones for patients on the ketogenic diet provides a gold-standard biofeedback marker that is objective and quantifiable for adherence. Deviation from the dietary standards of a well-formulated ketogenic diet will cause rapid decreases in ketones and elevations in blood glucose,

which will be identified in the patient:researcher interaction. For the standard diet arm, this will present a greater challenge. We will ask participants to inform us of dietary deviations and these will be identified and logged. The monthly self-report diaries will be used for tracking any minor adverse effects (GI distress, bloating, gut distension, diarrhea etc.). If participants do not experience any side effects, it is possible they will not have a self-report diary to share monthly.

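### The random-intercept model, as normally fitted, gives ketones one variance for both diets and all visits, so the week 8 and 16 ketone intervals can be miscalibrated

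*Protocol*

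**What the plan says.** Section 17.0 analyses glucose and ketones by "mixed effects linear regression with fixed effects for timepoint, diet group, their interaction, BMI, and sex". The covariance is given in one sentence: "We will use subject-level intercept random effects to account for correlation between repeated measurements within subjects". No variance specific to an arm or visit is mentioned. On timing, "Measurements will be taken at baseline, 8 weeks, and 16 weeks", and "The primary targets of inference are the treatment effects at each (post-baseline) timepoint". Whether such an effect is a difference in level or in change from baseline is not stated. In general "hypothesis tests will be two-sided and at the 5% significance level", and for the four primary comparisons "we will use a 4-way Bonferroni-Holm correction to account for multiplicity".

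On ketone levels, Section 8.2 says "BOHB levels in individuals consuming more than 100 grams of carbohydrate per day are usually ≤ 0.1 mmol/L" and describes "nutritional ketosis, which starts at 0.5 mM and extends up to approximately 3.5 mmol/L". The Dietary Interventions text in Section 7 gives a similar off-diet figure. Section 6.0 allocates 12 patients to each diet. The Power Analysis in Section 17.0 takes a ketone change of mean 0.6 and SD 0.16 mmol from a single-arm ketogenic study. No ketone SD is given for the AICR arm or by visit.

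The protocol is not consistent on whether baseline precedes the diet:
- The Dietary Interventions text starts the supplied meals four to seven days before baseline testing, so that the ketogenic arm is in ketosis by then.
- Section 8.1 places the first clinic evaluation before the intervention begins.
- Section 13 provides for patients who have baseline measures but never received the intervention.
- The Power Analysis works with change from baseline and a mean ketone change of 0.6 mmol, which presupposes a baseline before ketosis.

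**The concern.** A mixed model with only a random intercept and a common residual assigns one variance to all six arm-by-visit cells and one correlation to every pair of visits. Ketones do not behave like that. In the AICR arm, values sit close to zero and have almost no room to vary; in ketosis they can spread over several mmol/L. The model averages small and large variances and applies the average to the week 8 and 16 comparisons. If more small-variance cells enter the average than belong in the comparison, the standard error is too small. At stake are the stated precision of a primary endpoint and the variance estimates on which a later trial would be planned.

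**Working it through.** **1. The plan's own figure.** A two-sample t-test with 12 per arm, 22 df and two-sided alpha 0.0125 has noncentrality 0.34 / (0.16 × sqrt(2/12)) = 5.21 for ketones and 2.3 / (1.077 × sqrt(2/12)) = 5.23 for glucose. Power is 98.99% and 99.05%, so the stated 99% reproduces.

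**2. Level difference, complete data.** With balanced data the model's total variance settles at the mean of the six cell variances.
- Model variance of the difference: (2/12) × mean cell variance.
- True variance: (ketogenic variance + AICR variance) / 12 at that visit.
- Inputs: on-diet ketogenic SD 0.16 (the stated SD of change, used here as an assumed SD of level); off-diet SD 0.03 or 0.05 (assumed).

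Pre-diet baseline, off-diet SD 0.03:
- Mean cell variance (4 × 0.0009 + 2 × 0.0256)/6 = 0.00913; model SE sqrt(0.00913/6) = 0.0390.
- True SE sqrt((0.0256 + 0.0009)/12) = 0.0470.
- Ratio of model SE to true SE: 0.83. With off-diet SD 0.05 it is 0.85.

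Ketogenic arm in ketosis at baseline, same SD as later:
- Mean cell variance (3 × 0.0256 + 3 × 0.0009)/6 = 0.01325; model SE sqrt(0.01325/6) = 0.0470. Ratio 1.00.

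**3. Between these extremes.** With AICR variance near zero, ketogenic variance vB at baseline and v later, the ratio is sqrt((vB/v + 2)/3). It is 0.82 for vB = 0, 0.87 if the baseline SD is half the later SD, 0.90 if it is two thirds, and 1.00 if they are equal. It exceeds 1 if baseline ketosis is the more variable.

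**4. Difference in change, pre-diet baseline.** The model variance is 4 × residual variance / 12. The residual variance is the average over arms of (mean visit variance minus mean between-visit covariance). With off-diet SD 0.03 and within-subject correlation 0.5:
- Ketogenic arm 0.01737 − 0.00587 = 0.0115; AICR arm 0.00045; average 0.005975; model variance 0.00199.
- True variance (0.0217 + 0.0009)/12 = 0.00188. Ratio 1.03.

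At correlation 0.2 the ratio is 1.10 and at 0.8 it is 0.92.

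**5. Simulation with the full fixed-effects model.** REML fit, 1,500 trials per setting, off-diet SD 0.03, correlations 0.2, 0.5 and 0.8, assumed dropout shown as ketogenic/AICR. The Monte Carlo standard error near 90% coverage is sqrt(0.9 × 0.1/1500) = 0.8 points. Week 16, nominal 95%:

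| Baseline | Dropout | Level: SE ratio | Level: coverage | Change: SE ratio | Change: coverage |
|---|---|---|---|---|---|
| Pre-diet | 0/0 | 0.82-0.83 | 89.5-89.8% | 0.90-1.08 | 91.7-95.9% |
| Pre-diet | 6/2 | 0.64-0.67 | 79.1-81.7% | 0.73-0.77 | 84.2-85.3% |
| In ketosis | 0/0 | 0.98-0.99 | 94.1-95.3% | 0.99-1.00 | 94.4-94.6% |
| In ketosis | 4/4 | 0.97-0.98 | 93.8-94.3% | 0.98-1.00 | 93.7-94.0% |
| In ketosis | 6/2 | 0.84-0.92 | 90.7-92.9% | 0.83-0.84 | 87.9-88.9% |

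With equal variances everywhere (correlation 0.5), coverage was 94-96%, so the shortfall comes from the unequal variances.

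A larger simulation of 40,000 trials used a pre-diet baseline, off-diet SD 0.05, on-diet SD 0.16, 0.5 or 0.75, and no BMI or sex. For the week 16 level it gave an SE ratio of 0.80-0.84, coverage of 87.6-89.9% at nominal 95%, and 94.8-96.2% at nominal 98.75%. For change, 95% coverage was 91.1-95.6%. A Welch comparison at the visit covered 94.8-95.1%.

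**The case against.** A reader might infer that the ketone intervals are simply too narrow. The documents do not support that without conditions. Read as written, the Dietary Interventions text makes the ketogenic baseline an on-diet measurement. With 12 patients in each arm, pooling a variable arm with a quiet one leaves the standard error of their difference correct, so complete data then give about nominal coverage. For the change contrast, which is the one the Power Analysis uses, the error can go in either direction even with a pre-diet baseline. The range from 0.5 to about 3.5 mmol/L defines ketosis and is not a distribution of patients; the off-diet SDs and the dropout are assumptions. Section 17.0 also does not forbid a residual variance that differs by arm, and that detail could stand in an analysis plan that is not shown.

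All of this stands, and it limits the point to a conditional one. It does not remove it. Sections 8.1 and 13 and the Power Analysis point to a pre-diet baseline. Even under the Dietary Interventions text, nominal coverage needs a baseline after a few days of supplied meals to be as variable as weeks 8 and 16 of self-managed eating. Balance between arms is not assured either: Section 11 removes patients with severe diet-related reactions, and the Adherence and Retention text expects compliance problems. Higher ketogenic dropout is plausible, though not stated.

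A second tempting inference is that the ketone test is unsafe. The expected change is 0.6 mmol against a detectable 0.34. With an SD of 0.16 it is 0.6/0.047 = 12.8 true standard errors, so an error of this size would not plausibly reverse the result. If the diets truly did not differ, the arms would have similar variances and the distortion would be smaller.

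**Conclusion.** The point holds in conditional form. The equal-variance assumption is implausible for ketones on the protocol's own figures, and whether it does harm depends on the baseline, the contrast and the dropout.
- Pre-diet baseline, level contrast, complete data: standard error about 15-18% too small, 95% coverage about 88-90%.
- Ketogenic arm in ketosis at baseline with similar variance: about nominal on complete 12 v 12 data, 88-93% at week 16 with 6 v 2 dropout.
- Change contrast, pre-diet baseline, complete data: about 91-96%, with the direction set by the within-subject correlation.

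These sizes rest on assumed off-diet SDs of 0.03-0.05, on 0.16 used as an SD of level in the main calculations, and on assumed correlations and dropout. The consequence is for interval width and the variance estimates carried forward, not for the likely ketone test result. It should be fixed, but it does not invalidate the design.

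**What to change.** In Section 17.0, for ketones, let the residual variance differ by arm and visit, with small-sample degrees of freedom such as Kenward-Roger. Alternatively, prespecify an unequal-variance comparison (Welch or HC3) at weeks 8 and 16; this is also the natural fallback if the richer model does not converge with 24 patients. Keep the four-way Holm correction. Either route works whichever way the baseline timing is resolved.

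The cost is one sentence, a few more variance parameters and, in some cases, a somewhat wider ketone interval. Power is not threatened: a Welch test for 0.34 mmol at alpha 0.0125 with ketogenic SD 0.16 has more than 99.9% power with an AICR SD of 0.03-0.05, and 98.9% if the AICR SD is also 0.16.
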